The recruited participant will be asked to change into a gown appropriate to their radiological examination and then taken to a private room (x-ray room) to maintain dignity and privacy. They will then have various measures undertaken by the research team member (see instruction sheet appendix 3).

These will include:

- Height (m)
- Weight (kg)
- Body circumference
- Source-Object Distance (i.e. x-ray tube to patient skin, as a proxy for body diameter)

A small group of radiographers will be trained to undertake the specific study parameters to ensure consistent data collection (Appendix 4). They will then continue with the radiographic examination as requested by the referring clinician.

Data analysis

The data collected will allow modelling of the change in patient body shape between the two projections. Variations in shape between BMI subgroup, gender and age will be assessed. Mean and standard deviations will be calculated if the resultant data are approximately normally distributed and median (ISR) measures will be determined for non-parametric data.

[figure not shown]
Phase Two: Phantom Experiment

An anthropomorphic phantom of the abdomen and pelvis will be used to investigate the optimal image acquisition protocol based on the anatomical changes identified in phase one. No patients will be recruited for this part of the study.

The outcome of the phantom study will be specific kV and mAs settings or automatic exposure control (AEC) settings for the different techniques and comparison of the phantom dose data with national diagnostic reference levels.

Based on the variation in mean measures between the different position and body habitus in phase one a Kyoto phantom will be physically altered with the addition of appropriately positioned soft tissue density mimicking material. This will enable multiple exposures of the phantom to be made at different distances and exposure factors to ascertain whether automatic exposure devices can be reliably used in both of the patient positions or whether specific exposure charts should be calculated regarding a patient's body habitus.

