An example of the acquisition procedure is demonstrated in figure 2 below. The resultant images will be analysed for quality in relation to visualisation of the bony anatomy of the pelvis and hip joint. Based on a previously validated technique²⁶ radiation dose (entrance surface dose (ESD) and effective dose (ED)) will be calculated using a commercially available computer software system which utilises Monte Carlo code dose simulation (PCMXC). Calculations require the source-object distance, mAs and peak tube potential values (kV) to be entered for each data point.

Phase Three: Pelvic Radiograph Acquisition

This phase will compare radiographs obtained on the same patient in two different positions, supine and erect. The supine positioning is that which is currently undertaken within the imaging department. The erect positioning technique and acquisition parameters will be informed by the earlier phases of the research.

Sample size

A single arm pilot study is planned with no attempt at this time to undertake sub-group analysis. A minimum of sixty patients will be recruited to this study based on the premise of the future trial demonstrating a 5% difference in pelvic tilt between the 2 projections (95% confidence interval), ²⁷ this exceeds 10% of the potential future trial requirements ^{28,29} and includes a minimum of 12 participants per subgroup. ³⁰

The future trial is estimated to require a minimum sample of 474, based on the same calculations. To allow for the inability to perform the erect x-ray, exclusion based on image quality and to enable sub-group analysis, it is planned that the sample recruited would be 800. The subgroup analysis for referral reason will comprise:

- 1. Young adult with hip pain (18-40)
- 2. Patient with evidence of hip dysplasia
- 3. Older adult referred with symptoms or diagnosis of OA
- 4. Previous hip replacement under monitoring

Inclusion criteria

All patients who attend for general radiography of the hip or pelvis from their general practitioner or outpatient clinic will be eligible for inclusion to the study. It is estimated that there are approximately 60 eligible patients per week attending any one hospital site within the study organisation.

Exclusion criteria

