Each patient will be radiographed in two positions, supine with a SID of 115 cm (current technique employed within the imaging department) and erect with a SID of 180cm (new comparison technique). Additionally the patient will have their height and weight measured to confirm the appropriate exposure parameters established in phase two.

The supine and erect radiographic examinations will be performed in a random order with the preprinted data collection sheets indicating the order of the patient. This will be established using a random number generator. This procedure ensures that the patient preference cannot be related to the examination order.

Data collection and management

A data collection sheet will be used to record information about each study participant and the imaging parameters (Appendix 7). The data includes the anatomical measures (phase one and three) and exposure parameters (phase three only) and the patient will be asked their preference for the imaging technique (erect or supine). The data will be transcribed as soon as practicable into the Trust research management system EDGE with patient identifiable data being removed.

The additional erect pelvis projection will be stored on the MYT PACS system. Additionally anonymised copied will be stored to a study teaching file on PACS using their unique study identifier to allow blinded image review. The PI is a PACS administrator and will ensure this data is securely managed.

On completion of the recruitment data validation will take place to ensure there are no transcription errors and missing data. The final data set will be exported into Microsoft Excel for analysis. Further statistical analysis will take place using PCMXC and SPSS.

Data analysis

The phase three data will allow the comparison of the radiation dose (entrance surface dose (ESD) and effective dose (ED)) will be calculated using a commercially available computer software system which utilises Monte Carlo code dose simulation (PCMXC). Calculations will use the source-object distance, mAs and peak tube potential values (kV) for each exposure.

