Appendix 3. Phase 1: Data collection instructions

A study to compare supine and erect pelvis radiographs – assessment of impact on radiation dose and diagnostic markers (SEPRAIDD)

Preparation

Patient will have been greeted by a GCP trained radiographer who will introduce themselves and explain the study, prior to obtaining consent. If consent is gained then the patient will complete paperwork and be asked to change in to a gown as required for their examination.

If the examining radiographer is different to the one obtaining consent repeat ID checks should be undertaken following introduction of self. Confirmation of participant agreement to proceed should be sought verbally.

Study procedure

Height and Weight should be undertaken on the study calibrated weigh scale, in cm and kg.

A disposable 150cm tape measure should be used to measure body circumference at the levels of the lower costal margin, the iliac crests and the greater trochanter. Source-patient distance will be measured using the built in tape measure on the x-ray tube within the room.

- 1. The patient should be positioned AP against the erect bucky. The tape is passed around their body, the appropriate landmark palpated ensuring that the tape is parallel to the floor. The measurement should be taken whilst the patient is in arrested expiration and recorded on the data collection sheet. This is repeated for all three anatomical levels.
- 2. The patient should be asked to remain in the same standing position whilst the tube head is positioned at 115cm SID. The light beam is used to centre the tube at the level of the iliac crests. Measurements are taken, using the built in tape measure at the tube head, in the midline at the level of the lower costal margin, iliac crests and greater trochanters (to correlate with tape measure circumference readings). Arrested expiration should again be utilised.

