Appendix 7. Phase 3: Data collection sheet

A study to compare supine and erect pelvis radiographs – assessment of impact on radiation dose and diagnostic markers (SEPRAIDD)

Study ID Number:			Imaging order
Patient Hospital Number:			
Height:	m _	Weight:	kg
Age:		Gender:	M / F
Supine radiograph Start time:	Repe	at Yes/No	
kV	kV _		
mAs	mAs		
DAP	DAP		
EI Image time:	EI		
Erect radiograph Start time:	Сог	nments:	
kV			
mAs			
DAP			
EI Image time:			
Patient preference			
Supine / Erect			

Radiographer code:

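### Phase three dose is to be calculated from source-object distance for each exposure, but neither the phase three procedures nor the Appendix 7 sheet records that distance

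*Protocol*

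**What the plan says.** The phase three data analysis section says that ESD and ED will be obtained from Monte Carlo software, and that "Calculations will use the source-object distance, mAs and peak tube potential values (kV) for each exposure". The phase two text describes the same software in stronger terms: "Calculations require the source-object distance, mAs and peak tube potential values (kV) to be entered for each data point". The phase one list of measures defines the quantity as "Source-Object Distance (i.e. x-ray tube to patient skin, as a proxy for body diameter", so it depends on the patient and on posture.

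The phase three study procedures fix the source-image distance (SID) only: "supine with a SID of 115 cm (current technique employed within the imaging department) and erect with a SID of 180cm (new comparison technique". The one body measurement they add is this: "Additionally the patient will have their height and weight measured to confirm the appropriate exposure parameters established in phase two". The data management section then says of the collected data: "The data includes the anatomical measures (phase one and three) and exposure parameters (phase three only").

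Appendix 7 is the sheet named for phase three recording. It has identifiers, imaging order, height, weight, age, gender, patient preference and radiographer code. For the supine exposure, and again for a repeat, it has kV, mAs, DAP and EI. The erect block, which opens "Erect radiograph Start time", has the same four. Start and image times are recorded for each position. No field holds a distance, circumference or diameter.

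**The concern.** The Protocol fixes both the dose calculation and the form that feeds it, and the two disagree. A statistical analysis plan can choose a model or a summary measure, but it cannot supply a reading that nobody took.

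Dose is the first key research question. The Ethical Consideration section justifies exposing each participant twice on the ground that the alternatives could not show change within an individual. The Background names reduced soft-tissue compression and overlying abdominal tissue as the reasons why posture might alter dose. Both act through the thickness of the patient in each position. If source-object distance is predicted from height and weight, every patient of the same build receives the same assumed change in thickness. That part of the posture effect on ESD is then carried over from phase one and not observed in phase three.

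**Working it through.** The plan gives no figure to reproduce. The check has three steps.

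**1. Stated inputs against recorded fields**

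| Input to ESD and ED | Phase three procedures | Appendix 7 |
|---|---|---|
| kV, each exposure | exposure settings | recorded (supine, repeat supine, erect) |
| mAs, each exposure | exposure settings | recorded (supine, repeat supine, erect) |
| Source-object distance, each exposure | not measured; only SID is fixed | no field |

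Two of the three inputs are captured. The statement that phase three data include anatomical measures is met on the sheet by height and weight only. The form was read by a program, but its fields run in order from study number to radiographer code, and nothing suggests that a distance field was lost.

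**2. Can phase one fill the gap?**

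The Appendix 4 sheet does record source distance, at three body levels in each position. It does so for a separate cohort of 180. The erect reading is taken "whilst the tube head is positioned at 115cm SID", and the supine reading also at 115 cm. Converting to the 180 cm erect geometry is simple: for the same patient in the same position at the same detector, add 180 − 115 = 65 cm.

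The obstacle is that these are other patients. Overlap is unlikely. Phase one participants go on to have their own radiographs, phase three excludes anyone with a pelvic x-ray in the preceding 6 months, and the Gantt chart runs from approval in October to the end of recruitment in February. A phase three value would therefore come from a prediction, and the Protocol gives no rule for one.

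**3. How much does the distance matter?**

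At fixed kV and mAs, ESD is proportional to 1/SOD², where SOD is source-object distance. If a wrong distance is used:

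calculated ESD / true ESD = (true SOD / SOD used)²

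Assumption, not in the documents: patient thickness plus the gap to the detector is 30 cm. True SOD is then 115 − 30 = 85 cm supine and 180 − 30 = 150 cm erect.

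| SOD used is | Supine ESD | Erect ESD | Erect/supine ratio, same error in both |
|---|---|---|---|
| 4 cm too short | (85/81)² = 1.1012, +10.1% | (150/146)² = 1.0555, +5.6% | 1.0555/1.1012 = 0.959, −4.1% |
| 4 cm too long | (85/89)² = 0.9121, −8.8% | (150/154)² = 0.9487, −5.1% | 0.9487/0.9121 = 1.040, +4.0% |
| 2 cm too short | (85/83)² = 1.0488, +4.9% | (150/148)² = 1.0272, +2.7% | 1.0272/1.0488 = 0.979, −2.1% |
| 2 cm too long | (85/87)² = 0.9546, −4.5% | (150/152)² = 0.9739, −2.6% | 0.9739/0.9546 = 1.020, +2.0% |

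If the prediction is right supine but misses a 4 cm change on standing, the ratio moves by the erect error alone, −5.1% to +5.6%.

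Fixed SID is not a substitute for SOD. With thickness from 15 to 35 cm and a detector gap of 0 to 10 cm (both assumed), ESD at the same kV and mAs differs between the thinnest and thickest patient by a factor of 1.56 to 1.65 supine and 1.30 to 1.32 erect. With a 5 cm gap, for example, the factors are (95/75)² = 1.60 and (160/140)² = 1.31.

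**The case against.** A reader might go further than the documents allow in four ways.

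- **That the dose question cannot be answered.** This does not follow. kV, mAs and DAP are recorded for each patient and exposure, so measured within-patient dose information remains. What fails is the ESD and ED calculation as described.
- **That DAP is collected and ignored.** The phase three analysis plans a descriptive account of the acquisition parameters, which naturally covers DAP. It is fair to say only that DAP is not named as a dose outcome or as an input.
- **That phase one readings are unusable because they were taken at 115 cm SID.** The difference is a fixed 65 cm offset. The separate cohort is the difficulty.
- **That the posture comparison could be out by 10%.** That is a per-exposure figure. An error shared by both positions partly cancels, leaving about 4%. Errors independent between patients also average out: 10% per patient over 60 patients is 10/√60 ≈ 1.3% on the mean. A systematic error would not average out, but nothing in the documents shows that there would be one.

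It can also be argued that the text on anatomical measures in phase three means that source-object distance was intended there, and that only the form is out of step. That is possible. But the phase three procedures name only height and weight, so text and form still have to be reconciled. A rule for deriving the distance might sit in an analysis plan not seen here, but it would yield a modelled value, not one for each exposure.

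Finally, this is a pilot whose listed objectives are procedures and recruitment. That limits the harm. It also makes a data sheet that does not serve the stated analysis a fault in one of the things the pilot is meant to develop.

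**Conclusion.** The conflict stands. The Protocol states a per-exposure ESD and ED calculation with three inputs, and the phase three procedures and form record two of them. The calculation cannot be done as stated. Any substitute distance would be modelled from other patients, at the cost of the individual posture-related change in thickness.

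The size is moderate. For a 4 cm error it is about 9–10% in supine ESD, 5–6% in erect ESD, and about 4% in their ratio if both positions share the error. These figures rest on assumed distances of 85 and 150 cm, an assumed error, and the inverse-square law at fixed kV and mAs. They cover ESD only; no figure was worked out for ED. The matter should be settled before phase three recruitment, because an unrecorded distance cannot be recovered afterwards.

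**What to change.** 1. Add a source-to-skin distance field to Appendix 7 for each exposure: supine, any repeat supine, and erect. That is three fields, since the erect view is taken once only.
2. Add the reading to the phase three study procedures: taken at the centring point with the tube-head tape, as in phase one. Phase one uses that tape only at 115 cm SID, so confirm that it also serves at 180 cm.
3. Bring the sentence on anatomical measures in phase three into line with what the form then holds.
4. In the phase three data analysis, name the recorded DAP as a reported dose outcome beside ESD and ED.

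The cost is a brief extra tape reading per exposure, three fields on the sheet and a few sentences of text. The radiographers are already trained in this reading for phase one.

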The inconsistent radiographic technique and centring points have also been highlighted by patient exclusions in orthopaedic research studies because radiographs do not meet pre-determined positional and quality criteria. Interestingly, issues of radiographic technique were also identified in the 2014 NICE guidelines for hip OA³ which states that differing radiographic protocols contribute to a lack of robust evidence around their use. Radiography textbooks are also contradictory, resulting in local variation. Indeed one textbook suggests flexing a patients' hips and knees slightly to correct for pelvic tilt, a factor unlikely to be appreciated by clinicians, with potential to lead to misinterpretation.

Importantly, no previous study has considered the radiation dose implications of patient posture or defined the standardised positioning required to introduce this as a mainstream investigation. Patient position has potential to influence radiation dose through reduced soft-tissue compression and increased overlying abdominal tissues. This would have significant implications for image quality, which in turn could impact on clinical decision making. National dose reference levels (DRLs) do not exist for erect positioning, a non-standard technique, meaning that there is no parameters for dose in this projection, despite a small number of Trusts already adopting this technique. Interestingly, authors have demonstrated opportunities to reduce radiation dose with increased distance or orientation on digital equipment, but these were only undertaken supine using an anthropomorphic phantom^{24,25,26} and have not been translated into clinical practice. As a result this research hopes to develop a patient centred evidence base for the positioning and exposure factors for erect AP pelvis projections.

Key research questions

The key research questions requiring an answer are:

- 1. Does pelvic radiography performed in the erect position result in an increase in radiation dose to the patient?
- 2. Does pelvic radiography performed in the erect position demonstrate clinically significant changes in image quality when compared to a supine X-ray image?
- 3. Are erect pelvic radiographs acceptable to patients in their performance?
- 4. Would the change impact on service delivery, in terms of examination time?

Aims

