Descriptive analysis of the participant demographics and the image acquisition parameters will be undertaken, including patient preference and thematic analysis of any free text comments from the radiographer or patient. Comparison of examination length will be undertaken utilising the 'start time' and the time on the last image in that orientation, it is acknowledged this outcome will be influenced by the need for repeat exposures and technical difficulties in this small cohort.

Initial image quality will be assessed in relation to the diagnostic value of the radiograph and whether a repeat x-ray would have been warranted, this will allow comparison of repeat rates for the 2 examinations as well as the reasons. Further assessment of image quality will use a previously validated psychometric scale³¹ to compare the noise at different anatomical regions. This will provide a comparison between the 2 projections, the images will be randomly allocated for analysis and reviewers will be blinded to the acquisition technique (erect or supine) for this analysis to reduce bias and maintain objectivity.

Ethical Consideration

The key ethical issue associated with this research is the requirement for an additional x-ray in phase three. Other options have been explored including using only an anthropomorphic phantom and randomization of patients to either examination. These strategies do not provide sufficient robustness to demonstrate changes on an individual basis and the phantoms have fixed bony and soft tissue anatomy and therefore do not allow comparison of changes related to posture.

REC and HRA approval will be sought to ensure the additional radiation dose is managed within an appropriate framework. This will include establishing protocols to limit radiation exposure through exclusion from the study if repeat x-rays are required due to quality reasons. A patient will only have one radiograph taken in the erect position, regardless of final image appearances. This will ensure that the maximum additional dose for a single patient is limited to one exposure whilst maintaining the integrity of their clinical examination. This will also provide information regarding the potential repeat rate for erect radiographs in a prospective future trial. The study team will then decide whether the patient is excluded from the study, included for limited analysis or fully included despite imaging appearances, on a case by case basis.

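### Blinding is stated for the noise reading but not extended to the diagnostic-value and repeat-warranted rating used to compare erect with supine images

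*Protocol*

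**What the plan says.** The Protocol, Phase Three, Data analysis, describes two assessments of image quality, one after the other.

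- **Initial assessment.** "Initial image quality will be assessed in relation to the diagnostic value of the radiograph and whether a repeat x-ray would have been warranted". Its purpose is comparative: "this will allow comparison of repeat rates for the 2 examinations as well as the reasons". No rater, timing or blinding is given.
- **Further assessment.** A previously validated psychometric scale is used "to compare the noise at different anatomical regions". The sentence that follows says images will be randomly allocated and that "reviewers will be blinded to the acquisition technique (erect or supine) for this analysis to reduce bias and maintain objectivity".

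Research question 2 (Key research questions) asks whether erect radiography will "demonstrate clinically significant changes in image quality when compared to a supine X-ray image".

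Three other places bear on the point. Data collection and management says anonymised copies are kept "using their unique study identifier to allow blinded image review". Ethical Consideration allows one erect exposure only, whatever the image looks like, and expects this to inform the repeat rate for a future trial. Appendix 7, the phase three data sheet, has a Repeat Yes/No field and a second set of exposure fields in the supine block; the erect block has only a comments field.

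**The concern.** Research question 2 concerns clinically significant image quality. Of the two phase three assessments, the rating of diagnostic value and repeat need is the closer to that question. It is a global judgement, and one of the two techniques is new and is the reason for the study. A rater who knows which image is erect may be more lenient or stricter with it. The protocol's own reason for blinding, to limit bias and keep the reading objective, applies at least as strongly to this judgement as to a noise scale, yet the stated blinding does not reach it.

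At stake are the erect-versus-supine comparison of diagnostic value and repeat rates in this pilot, and the planning of the larger trial, because the erect repeat rate is meant to carry forward.

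**Working it through.** The protocol gives no figure for the image-quality comparison, so there is nothing to reproduce. The check is a reading of every place that mentions blinding, image-quality assessment or repeats.

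1. **What the blinding sentence refers to.** The order in Data analysis is: initial rating, use of that rating to compare repeat rates, further assessment of noise, then random allocation and blinding. The blinding sentence limits itself to a single analysis, and its nearest antecedent is the noise comparison. The protocol separates the two assessments by calling one initial and the other further.

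2. **Other mentions of blinding.** The only other one is in Data collection and management ("using their unique study identifier to allow blinded image review"). It describes how images are stored and names no rating, so it neither extends nor restricts the blinding.

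3. **Status of the initial rating.** Data analysis does not say who makes it, when, or with what knowledge of position. The accurate statement is that blinding is not extended to it.

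4. **Whether the two repeat rates measure the same thing.**

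| | Supine | Erect |
|---|---|---|
| Can a repeat be taken? | Yes; Appendix 7 has a field and exposure values for it | No; Ethical Consideration limits it to one exposure |
| What a repeat is | An event recorded at the examination | A judgement that one would have been warranted |
| Is position known when it is recorded? | Yes | Not stated |

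 Unless a common rating is defined, operator events in one position may be set against opinions in the other.

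5. **An added exposure to the same risk.** Under Ethical Consideration, the study team decides individually, after the erect image has been seen, whether a patient is excluded, partly analysed or fully included. No blinding is stated for that decision, and it affects which images enter the comparison.

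6. **Sensitivity to single calls.** Input: a minimum of 60 patients (Phase Three, Sample size), each giving one first exposure per position. One changed call on an erect image moves the erect rate, and so the erect-minus-supine difference, by 1/60 = 0.0167, or 1.7 percentage points. This assumes all 60 contribute. It shows how sensitive the comparison is and does not estimate a bias.

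**The case against.** The strongest reply is that silence is not a statement. The protocol nowhere says that the initial rating is made by people who know the position. The anonymised file is set up for blinded review without being limited to noise, and a looser reading could let it cover both assessments. The conditional wording of the initial rating could also mean one retrospective judgement applied to both images. These points stand in part. A reader might infer that the diagnostic rating is done unblinded, and the documents do not support that. They leave the matter open, and the one sentence that fixes the scope of blinding points to the noise reading.

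A reader might also infer that the blinded reading would miss an erect image with equal noise but hidden anatomy, especially since phase two judges images on "visualisation of the bony anatomy of the pelvis and hip joint" and phase three does not repeat that criterion. The documents do not support this either. The scale is cited from a source that is not at hand, and its listed title concerns image quality generally, so its items cannot be assumed. The Background links posture to dose through tissue compression and overlying tissue, and from there to image quality; it does not say that the joint is obscured. The initial rating of diagnostic value would in any case address such an image. The issue is how that rating is made, not that its content is missing.

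Finally, masking may not work fully. The two techniques differ in source-image distance (115 cm supine, 180 cm erect, under Study procedures), and the Background reports that pelvic tilt changes with posture, so trained readers may guess the position. Real supine repeats cannot be blinded at all. Both are limits on the remedy. Neither is a reason to leave the rating outside the blinding when the noise reading, which has the same difficulty, is inside it.

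**Conclusion.** The point holds in this form: random allocation and blinding to position are stated for the noise reading and not extended to the rating of diagnostic value and repeat need, although that rating is closest to research question 2 and is used to compare the two examinations. The asymmetry between recorded supine repeats and hypothetical erect ones makes the comparison harder to interpret.

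The conclusion rests on the plain reading of the blinding sentence. If the sponsor intended both ratings to be blinded, the plan is sound on the blinding point and only the text needs correcting; the definition of a repeat in each position would still need stating.

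The size of any bias cannot be given. The protocol states no expected repeat rate, and any assumed rate or number of miscalls would be invention; all that follows from the document is that each call is worth 1.7 percentage points among 60. Nor does the point require diagnostic value to be ranked above noise: the protocol ranks no outcome under research question 2, and as a pilot it need not. The change is worth making because it is cheap and protects a comparison that the protocol says it will make.

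**What to change.** Amend Phase Three, Data analysis, to state that:

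- the same blinded reviewers, in the same randomised reading of the anonymised images, rate diagnostic value and repeat warranted (yes/no, with the reason) for every participant on the first exposure in each position;
- these blinded ratings are used for the erect-versus-supine comparison;
- actual supine repeats, as recorded on the Appendix 7 sheet, are reported separately as an operational outcome and are not set against the erect judgements.

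For this to work, the anonymised file must hold the first exposure in both positions, including a supine first exposure that was later repeated. Data collection and management should say so.

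The change needs no extra patients, exposures or readers, and does not alter how any examination is carried out. It costs a few more items per image, so slightly longer reading. Masking may be imperfect because posture can alter the appearance of the image; asking reviewers to guess the position would show how far it held.
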